#### 10.1.8 General remarks – important

Because of lacking analytical coverage beyond the instructed preparation procedure of the different dose formulations, no further (external) dilutions of the reconstituted solutions are allowed.

The present reconstitution instruction does not contain any advice how to withdraw a specific dose from the reconstituted solutions. The specific dose volumes to be withdrawn from the described dose formulations in order to obtain a required dose will be calculated and documented by TMCP in the Clinical Trial Protocol (CTP) and subsequent documents (e.g. work sheets).

c26547838-07 Trial Protocol Page 96 of 102

Proprietary confidential information © 2020 Boehringer Ingelheim International GmbH or one or more of its affiliated companies

# 11. DESCRIPTION OF GLOBAL AMENDMENT(S)

# 11.1 GLOBAL AMENDMENT 1

Date of amendment	15 May 2019		
EudraCT number	2019-000888-25		
EU number			
BI Trial number	1425-0001		
BI Investigational Medicinal	BI 706321		
Product(s)			
Title of protocol	Safety, tolerability, and pharmacokinetics of single rising oral doses of BI 706321 in healthy male subjects (single-blind, randomised, placebocontrolled, parallel group design)		
Authorities	approval of the IRB / IEC / Competent		
	ly in order to eliminate hazard – IRB / IEC / Lified of change with request for approval		
	RB / IEC / Competent Authority approval as		
changes involve logistical or ad			
Section to be changed	
 
Synopsis, Flow Chart, Sections 1.3.3.1, 1.4.4, 3.1, 3.3, 4.1.1, 4.1.4, 7.3.2, 7.7
 
Flow Chart, Sections 3.3.4.3, 5.2.4.1,
 
Flow Chart, Sections 1.4.3, 2.2.2.1, 3.3.2, 3.3.3, 5.2.1, 5.2.2,
 
Sections 3.1, 3.3.5
 
Sections 1.3.3.2, 3.1, 4.1.4
 
Flow Chart
 
Section 5.4
 
		
Description of change	
 
Addition of dose groups 0.6 mg and 2 mg.         
 
For logistical reasons (agreement with other trial documentation), these additional dose groups receive dose group numbers 9 and 11.
 
Number of subjects planned to be entered into the trial adjusted to 80 (maximal 96 in case of additional dose groups)
 
 
 
Change of dose escalation stopping criterion 5 in Section 3.3.4.3: Escalation will now be stopped if at least 2 subjects on active treatment at one dose level demonstrate a confirmed QTc increase from baseline mean of greater than 60 ms.
 
		

07 July 2020

c26547838-07 Trial Protocol

Page 97 of 102

Proprietary confidential information © 2020 Boehringer Ingelheim International GmbH or one or more of its affiliated companies

	
 
For facilitation of implementation, all ECGs are done as single ECGs and not as triplicates.
 
3) Addition of oral body temperature to vital signs at select time points. Consideration of body temperature in inclusion criterion 1 and exclusion criterion 1.
 
4) At minimum, safety and tolerability data of 5 instead of 4 actively dosed subjects at the current dose level are needed for dose escalation to the next higher dose level
 
5) Dose groups 40 mg and 60 mg will only be dosed after approval of a substantial amendment.
 
6) Minor change of planned times of pre-dose procedures on Day 1: Drug/alcohol screening at -2 h instead of at -1:30 h; urine PK pre-dose value at -1:30 h instead of at -2 h.
 
7) First paragraph: mRNA may be analysed instead of "will"
 

Rationale for change	
 
Request from competent authority / IEC
 
Request from competent authority / IEC
 
Request from competent authority / IEC
 
Request from competent authority / IEC
 
Request from competent authority / IEC
 
Request from competent authority / IEC
 
Logistical reasons (This allows that random number is allocated after drug / alcohol test and before urine PK)
 
Alignment of wording with the second-last paragraph of the same Section ("[] depending on these results a decision will be made []")
 

Page 98 of 102

Proprietary confidential information © 2020 Boehringer Ingelheim International GmbH or one or more of its affiliated companies

#### 11.2 GLOBAL AMENDMENT 2

Date of amendment	12 June 2019			
EudraCT number	2019-000888-25			
EU number				
BI Trial number	1425-0001			
BI Investigational Medicinal	BI 706321			
Product(s)				
Title of protocol	Safety, tolerability, and pharmacokinetics of single rising oral doses of BI 706321 in healthy male subjects (single-blind, randomised, placebocontrolled, parallel group design)			
To be implemented only after approval of the IRB / IEC / Competent Authorities				
	ly in order to eliminate hazard – IRB / IEC /			
	ified of change with request for approval			
	RB / IEC / Competent Authority approval as			
changes involve logistical or ad	ministrative aspects only			
	1) 5222			
Section to be changed	1) 5.3.2.3 2) 5.4.1			
Description of change	
 
Change of 10% Tween 20 volume per urine container from 10 mL to 2 mL
 
Specification of transport conditions and time window.
 
			
Rationale for change	
 
According to validation results, 2 mL 10%         Tween 20 solution is needed     
 
Information is needed for organisational reasons.
 
			

Page 99 of 102

Proprietary confidential information © 2020 Boehringer Ingelheim International GmbH or one or more of its affiliated companies

#### 11.3 GLOBAL AMENDMENT 3

Date of amendment	07 Aug 2019			
EudraCT number 2019-000888-25				
EU number				
BI Trial number	1425-0001			
BI Investigational Medicinal	BI 706321			
Product(s)				
Title of protocol	Safety, tolerability, and pharmacokinetics of single			
_	rising oral doses of BI 706321 in healthy male			
	subjects (single-blind, randomised, placebo-			
	controlled, parallel group design)			
	71 6 1 6 7			
	·			
To be implemented only after a	approval of the IRB / IEC / Competent			
Authorities				
To be implemented immediate	ly in order to eliminate hazard – IRB / IEC /			
_	Competent Authority to be notified of change with request for approval			
	RB / IEC / Competent Authority approval as			
changes involve logistical or administrative aspects only				
	•			
Section to be changed	Synopsis, 1.3.3.1, 3.1, 4.1.1, 4.1.4, 7.7			
Description of change	Escalation of dose levels will be changed:			
	Old: 0.3 - 0.6 - 1.2 - 2 - 4 - 8 - 15 - 25 - 40 - 60 mg			
	New: 0.3 - 0.6 - 1.2 - 2 - 4 - 8 - 20 - 40 mg			
Rationale for change	- Bioavailability is worse than expected			
9	- After escalation from 0.6 mg to 1.2 mg			
	exposure increased less than 35%			
	1			

Page 100 of 102

Proprietary confidential information © 2020 Boehringer Ingelheim International GmbH or one or more of its affiliated companies

#### 11.4 GLOBAL AMENDMENT 4

Date of amendment	06 Sep 2019		
EudraCT number	2019-000888-25		
EU number			
BI Trial number	1425-0001		
BI Investigational Medicinal	BI 706321		
Product(s)			
Title of protocol	Safety, tolerability, and pharmacokinetics of single		
	rising oral doses of BI 706321 in healthy male		
	subjects (single-blind, randomised, placebo-		
	controlled, parallel group design)		
To be implemented only after ap	oproval of the IRB / IEC / Competent		
Authorities	-		
To be implemented immediately	in order to eliminate hazard – IRB / IEC /		
Competent Authority to be notif	ied of change with request for approval		
	B / IEC / Competent Authority approval as		
changes involve logistical or administrative aspects only			
Section to be changed	Synopsis, 1.3.3.1, 3.1, 4.1.1., 4.1.4		
Description of change	With the exception of the total number of dose		
	groups all changes from Amendment 3 have been		
	removed in this Amendment 4. Thus the original		
	dose escalation schedule of CTP Version 3.0 will be		
	valid again: 0.3 - 0.6 - 1.2 - 2 - 4 - 8 - 15 - 25 - 40 -		
	60 mg		
Rationale for change	Global Amendment 3 specified conditions for		
	changing the escalation schedule. These conditions		
	are not given. Based on preliminary PK-data, dose		
	escalating from 8 mg to 20 mg would increase the		
	exposure of BI 706321 more than factor 2. Therefore,		
	the Global Amendment 4 is written to return to the		
	original dose escalation schedule (given in CTP 3.0).		
	The return to the original escalation schedule via		
	Non-Substantial Amendment under the given		
	conditions has been described in Amendment 3.		

Page 101 of 102

Proprietary confidential information © 2020 Boehringer Ingelheim International GmbH or one or more of its affiliated companies

#### 11.5 GLOBAL AMENDMENT 5

[figure not shown]
Date of amendment	16 Dec 2019	
EudraCT number	2019-000888-25	
EU number		
BI Trial number	1425-0001	
BI Investigational Medicinal	BI 706321	
Product(s)		
Title of protocol	Safety, tolerability, and pharmacokinetics of single	
	rising oral doses of BI 706321 in healthy male	
	subjects (single-blind, randomised, placebo-	
	controlled, parallel group design)	
ı v	approval of the IRB / IEC / Competent	
Authorities		
•	y in order to eliminate hazard – IRB / IEC /	
	ified of change with request for approval	
	RB / IEC / Competent Authority approval as	
changes involve logistical or ad	ministrative aspects only	
Section to be abanged	1.) Synopsis, Flow chart, Sections 1.2.3, 1.3, 1.4.3,	
Section to be changed	1.) Synopsis, Flow chart, Sections 1.2.3, 1.3, 1.4.3, 1.4.4. 1.4.5, 2.1.1, 2.1.2, 2.1.3, 2.2.2, 3.1, 3.2, 3.3.2,	
	3.3.5, 4.1.1, 4.1.2, 4.1.4, 4.1.5, 4.2.2.2, 5.2.1, 5.2.4.2,	
	5.3.2, 5.4, 6.1, 6.2.2, 7.1, 7.2, 7.3, 7.4, 7.6, and 7.7	
	5.5.2, 5.4, 6.1, 6.2.2, 7.1, 7.2, 7.5, 7.4, 7.6, and 7.7	
	3.) Section 1.2.2	
Description of change	1.) To implement Part II to the study protocol.	
1		
	3.) Residual effect period is reduced to 8 days	
	, ,	
Rationale for change	1.) Global Amendment 5 has been written to add a	
	Part II to the trial protocol. In Part II the relative	
	bioavailability of a tablet (compared to the capsule	
	tested in Part I) and the effect of food on tablet	
	bioavailability should be investigated to prepare	
	upcoming trials in patients (e.g. to advise a suitable	
	dosing regimen).	
l I	3.) Based on safety and PK-data obtained in Part I	

Page 102 of 102

Proprietary confidential information © 2020 Boehringer Ingelheim International GmbH or one or more of its affiliated companies

#### 11.6 GLOBAL AMENDMENT 6

Date of amendment	07 July 2020			
EudraCT number				
EU number				
BI Trial number	1425-0001			
BI Investigational Medicinal	BI 706321			
Product(s)				
Title of protocol	Safety, tolerability, and pharmacokinetics of single			
	rising oral doses of BI 706321 in healthy male			
	subjects (single-blind, randomised, placebo-			
	controlled, parallel group design)			
To be implemented only after	approval of the IRB / IEC / Competent			
Authorities	approval of the IKB / IEC / Competent			
To be implemented immediate	ely in order to eliminate hazard – IRB / IEC /			
	tified of change with request for approval			
Can be implemented without I	RB / IEC / Competent Authority approval as			
changes involve logistical or ac	dministrative aspects only			
Section to be changed	Section 3.3.3			
Description of change	A new exclusion criterion has been added to cover			
pandemic COVID-19.				
Rationale for change	Request of competent authority.			

2. LIST OF ABBREVIATIONS

See Medicine Glossary:
website: [glossary](#)

Term	Definition / description
ALT	Alanine Aminotransferase
ANCOVA	Analysis of Covariance
AST	Aspartate Aminotransferase
AUC _{0-∞}	Area under the concentration-time curve of the analyte in plasma over the time interval from 0 extrapolated to infinity
AUC _{0-tz}	Area under the concentration-time curve of the analyte in plasma over the time interval from 0 to the last quantifiable data point
BMI	Body mass index
cap	Capsule
CARE	Clinical Analysis and Reporting Environment
CI	Confidence Interval
C _{max}	Maximum measured concentration of the analyte in plasma
CV	Arithmetic Coefficient of Variation
DBLM	Database Lock Meeting
DILI	Drug induced liver injury
ECGPCS	ECG Pharmacokinetic Concentration Set
gCV	Geometric Coefficient of Variation
gMean	Geometric Mean
LLT	Lower Level Term
Max	Maximum
MedDRA	Medical Dictionary For Regulatory Activities
Min	Minimum
N	Number non-missing observations
NE	Neutrophil elastase
os	Oral solution
P10	10 th percentile
P90	90 th percentile
PDS	Pharmacodynamic parameter analysis set

Term	Definition / description
PKS	PK parameter analysis set
PT	Preferred Term
Q1	1 st quartile
Q3	3 rd quartile
QD	Quaque die, once daily
R	Reference
RAGe	Report Appendix Generator system
REP	Residual Effect Period
SD	Standard Deviation
SOC	System Organ Class
t _{max}	Time from dosing to maximum measured concentration of the analyte in plasma
T	Test
TS	Treated Set
TSAP	Trial Statistical Analysis Plan
ULN	Upper Limit of Normal
WHO-DD	World Health Organization Drug Dictionary

3. INTRODUCTION

As per ICH E9 ([1](#)), the purpose of this document is to provide a more technical and detailed elaboration of the principal features of the analysis described in the protocol, and to include detailed procedures for executing the statistical analysis of the primary and secondary variables and other data.

This trial statistical analysis plan (TSAP) assumes familiarity with the Clinical Trial Protocol (CTP), including Protocol Amendments. In particular, the TSAP is based on the planned analysis specification as written in CTP Section 7 “Statistical Methods and Determination of Sample Size”. Therefore, TSAP readers may consult the CTP for more background information on the study, e.g., on study objectives, study design and population, treatments, definition of measurements and variables, planning of sample size, randomisation.

Study data (including data entered in the RAVE EDC system and external data provided by suppliers) will be stored in a Clinical Data Repository (CDR). Pharmacokinetic (PK) parameters will be calculated using Phoenix WinNonlinTM software (version 6.3 or higher, Certara USA Inc., Princeton, NJ, USA).

The statistical analyses will be performed within the validated working environment CARE, including SAS[®] (current Version 9.4, by SAS Institute Inc., Cary, NC, USA), and a number of SASTM-based tools (e.g., macros for the analyses of AE data or laboratory data; Report Appendix Generator system (RAGe) for compilation/formatting of the CTR appendices).

4. CHANGES IN THE PLANNED ANALYSIS OF THE STUDY

All analyses as planned in the CTP will be performed and are described in more detail in this TSAP.

5. ENDPOINTS

5.1 PRIMARY ENDPOINTS

Section 2.1.2 of the CTP:

Part I: The primary endpoint for assessment of safety and tolerability of BI 706321 is the percentage of subjects with drug-related adverse events.

Part II: The following pharmacokinetic parameters will be determined for BI 706321:

- *AUC_{0-t_z} (area under the concentration-time curve of the analyte in plasma over the time interval from 0 to the last quantifiable data point)*
- *C_{max} (maximum measured concentration of the analyte in plasma)*

5.2 SECONDARY ENDPOINTS

5.2.1 Key secondary endpoints

This section is not applicable as no key secondary endpoints have been defined in the CTP.

5.2.2 Secondary endpoints

[figure not shown]
Section 2.1.3 of the CTP:

[figure not shown]
Part I: The following pharmacokinetic parameters will be determined for BI 706321 if feasible:

[figure not shown]
[figure not shown]
- *AUC_{0-∞} (area under the concentration-time curve of the analyte in plasma over the time interval from 0 extrapolated to infinity)*
- *C_{max} (maximum measured concentration of the analyte in plasma)*
- *t_{max} (time from dosing to the maximum measured concentration of the analyte in plasma)*

Part II: The following pharmacokinetic parameter will be determined for BI 706321:

- *AUC_{0-∞} (area under the concentration-time curve of the analyte in plasma over the time interval from 0 extrapolated to infinity)*

6. GENERAL ANALYSIS DEFINITIONS

6.1 TREATMENTS

It is planned that in total up to 80 healthy male subjects participate in this study.

In Part I 64 subjects are planned to be included, according to 8 sequential groups comprising 8 subjects per group. Within each dose group, 6 subjects will receive the active drug and 2 will receive placebo.

Two additional higher dose groups with BI 706321 40mg and 60mg (capsule) are considered and will only be dosed after approval of a substantial amendment.

In Part II 12 subjects are to be randomly allocated to one of 3 treatment sequences R-T1-T2, T1-T2-R or T2-R-T1. In addition, up to 4 replacement subjects may be included. There will be a washout period of at least 12 days between the treatments.

For details of dosage and formulation see Table 6.1:1 and [Table 6.1:2](#) below.

Table 6.1: 1 Labels for treatments for use in the CTR – Part I

Dose group	Sort order	Treatment	Short label
1, 2, 9	1	P*	Placebo, oral solution, po, qd
3-8, 11	2	R*	Placebo, capsule, qd
1	3	A	BI 706321, oral solution, 0.3 mg, qd
9	4	I	BI 706321, oral solution, 0.6 mg, qd
2	5	B	BI 706321, oral solution, 1.2 mg, qd
11	6	K	BI 706321, capsule, 2*1 mg, qd
3	7	C	BI 706321, capsule, 4*1 mg, qd
4	8	D	BI 706321, capsule, 8*1 mg, qd
5	9	E	BI 706321, capsule, 3*5 mg, qd
6	10	F	BI 706321, capsule, 5*5 mg, qd
7**	11	G	BI 706321, capsule, 2*20 mg, qd
8**	12	H	BI 706321, capsule, 3*20 mg, qd

*: The placebo group in the safety evaluation will consist of all placebo treated subjects, regardless of the dose group in which they were treated, but separated by pharmaceutical formulation (capsule and oral solution).

**: Dose groups 40 mg and 60 mg will only be dosed after approval of a substantial amendment.

Table 6.1: 2 Labels for treatments for use in the CTR – Part II

Treatment		Short label	Test/Reference
X	BI 706321, tablet, 2*2mg, qd, fasted	BI tab fasted	T1
Y	BI 706321, tablet, 2*2mg, qd, fed	BI tab fed	T2
Z	BI 706321, capsule, 4*1mg, qd, fasted	BI cap fasted	R

The following separate study phases will be defined for the analyses of AEs:

Part I:

- **Screening** (ranging from 0:00h (midnight) on day of informed consent until first administration time of study drug (BI 706321 or Placebo))
- **On treatment**
 - **BI/Placebo treatment** (separately for each treatment, ranging from the time of administration of BI 706321/Placebo until 0.00 h (midnight) on the day after trial completion date (planned 15-22 days after administration of BI 706321/Placebo))

Part II:

- **Screening** (ranging from 0:00h (midnight) on day of informed consent until first administration time of study drug in first study period (BI 706321))
- **On treatment**
 - **BI treatment** (labelled ‘BI tab fasted’, ‘BI tab fed’, ‘BI cap fasted’) (separately for each treatment, ranging from the time of first administration of BI 706321 in each period until next administration or 0.00 h (midnight) on the day after trial completion date, whatever occurs first)

Please note that all AEs reported between start of trial drug administration until end of individual's trial or until starting next treatment period will be considered on-treatment. Hence, on-treatment is defined until at least 15 days (Part I) and at least 8 days (Part II) after first treatment administration.

The following AE displays will be provided in the report:

Section 15.3 and Appendix 16.1.13.1.8 (for ClinicalTrials.gov and EudraCT) of the CTR displays:

In these displays, the on treatment phase will be analysed (labelled with the name of the study treatment (short label)). Screening will not be included in this analysis.

In section 15.3, the following totals will be provided in addition:

- a total over all BI treated phases ("BI Total") – Part I only
- a total over all placebo treated phases ("Plc Total") – Part I only
- a total over all on treatment phases included in this analysis ("Total")

In outputs for ClinicalTrials.gov and EudraCT both study parts will be combined in one table and the following totals will be provided:

- a total over all BI treated phases of Part I ("BI Total Part I")
- a total over all placebo treated phases ("Plc Total")
- a total over all on treatment phases of Part I ("Total Part I")
- a total over all BI treated phases of Part II ("BI Total Part II")
- a total over all on treatment phases included in this analysis ("Total")

In Section 15.4 and Appendix 16.2.7 (Listings) of the CTR displays screening will be included and no totals will be provided.

Tables of vital signs, ECG and laboratory values will present results by the above mentioned on treatment phase.

For detailed information on the handling of the treatments refer to Technical TSAP ADS (analysis data set) plan and Analysis Data Reviewers guide.

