#### 1.2.2 Residual Effect Period

The Residual Effect Period (REP) is the period after the last dose with measurable drug levels and/or pharmacodynamic effects still likely to be present. For BI 706321, a residual effect period has been determined at 8 days based on Part I. In Part 1, the conservatively, a minimum observation period of 2 weeks has been selected, i.e. the individual subject's end of trial is on day 15 following dosing at the earliest (see Flow Chart). In Part II it is at 8 days.

All AEs reported between administration of BI 706321 and the individual subject's end of trial will be counted as on-treatment AEs.

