## 5.2.3 Safety laboratory parameters

For the assessment of laboratory parameters, blood and urine samples will be collected by the trial site at the times indicated in the Flow Chart after the subjects have fasted for at least 10 h. For retests, at the discretion of the investigator or designee, overnight fasting is not required. The parameters that will be determined are listed in Tables 5.2.3: 1 and 5.2.3: 2. Reference ranges will be provided in the ISF, Section 10.

Manual differential white blood cell count or urine sediment examinations will only be performed if there is an abnormality in the automatic blood cell count or in the urinalysis, respectively.

c26547838-07 Trial Protocol

Page 56 of 102

Proprietary confidential information © 2020 Boehringer Ingelheim International GmbH or one or more of its affiliated companies

Table 5.2.3: 1 Routine laboratory tests

Functional lab group	BI test name [comment/abbreviation]	$\mathbf{A}^1$	B 	$\mathbf{C}^1$
Haematology	Haematocrit	X	X	X
-	Haemoglobin	X	X	X
	Red Blood Cell Count/Erythrocytes	X	X	X
	Reticulocytes, absol.	X	X	X
	Reticulocytes/Erythrocyte	X	X	X
	White Blood Cells/Leucocytes	X	X	X
	Platelet Count/Thrombocytes (quant)	X	X	X
Automatic WBC	Neutrophils/Leukocytes; Eosinophils/Leukocytes; Basophils/	X	X	X
differential, relative	Leukocytes; Monocytes/Leukocytes; Lymphocytes/Leukocytes			
Automatic WBC	Neutrophil, absol.; Eosinophils, absol.; Basophils, absol.;			
differential,	Monocytes, absol.; Lymphocytes, absol.	X	X	X
absolute				
Manual differential	Neut. Poly (segs); Neut. Poly (segs), absol.; Neutrophils			
WBC (if automatic	Bands; Neutrophils Bands, absol.; Eosinophils/Leukocytes;			
differential WBC is	Eosinophils, absol.; Basophils/ Leukocytes; Basophils, absol.;			
abnormal)	Monocytes/ Leukocytes; Monocytes, absol.;			
	Lymphocytes/Leukocytes; Lymphocytes, absol.			
Coagulation	Activated Partial Thromboplastin Time	X	X	X
	Prothrombin time	X	X	X
	Prothrombin time – INR (International Normalization Ratio)	X	X	X
	Fibrinogen	X	X	X
Enzymes	AST [Aspartate transaminase] /GOT, SGOT	X	X	X
•	ALT [Alanine transaminase] /GPT, SGPT	X	X	X
	Alkaline Phosphatase	X		X
	Gamma-Glutamyl Transferase	X		X
	Creatine Kinase [CK]	X	X	X
	Creatine Kinase Isoenzyme MB [only if CK is elevated]			
	Lactic Dehydrogenase	X	X	X
Hormones	Thyroid Stimulating Hormone	X		
Substrates	Glucose (Plasma)	X		X
	Creatinine	X	X	X
	Bilirubin, Total	X	X	X
	Bilirubin, Direct	X	X	X

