	Protein, Total	X		X
	C-Reactive Protein (Quant)	X	X	X
	Haptoglobin	X		X
	Ferritin	X		X
	Uric Acid	X		X
	Cholesterol, total	X		X
	Triglyceride	X		X
Electrolytes	Sodium	X	X	X
•	Potassium	X	X	X
	Chloride	X		X
	Calcium	X	X	X
	Phosphate (as Phosphorus, Inorganic)	X		X

A, B, and C are different sets of laboratory values. The Flow Chart defines at which time point which set is to be investigated.

 c26547838-07
 Trial Protocol
 Page 57 of 102

 Proprietary confidential information © 2020 Boehringer Ingelheim International GmbH or one or more of its affiliated companies

Table 5.2.3: 1 Routine laboratory tests (cont).

Functional lab group	BI test name [comment/abbreviation]	$A^1$	$B^1$	$C^1$
Urinalysis (Stix)	Urine Nitrite (qual)	X		X
	Urine Protein (qual)	X		X
	Urine Glucose (qual)	X		X
	Urine Ketone (qual)	X		X
	Urobilinogen (qual)	X		X
	Urine Bilirubin (qual)	X		X
	Urine RBC/Erythrocytes (qual)	X		X
	Urine WBC/Leucocytes (qual)	X		X
	Urine pH	X		X
Urine sediment	Only positive findings will be reported (for instance, the			
(microscopic	presence of sediment bacteria, casts in sediment, squamous			
examination if	epithelial cells, erythrocytes, leukocytes)			
erythrocytes,				
leukocytes nitrite or				
protein are abnormal				
in urine)				

A, B, and C are different sets of laboratory values. The Flow Chart defines at which time point which set is to be investigated.

The tests listed in Table 5.2.3: 2 are exclusionary laboratory tests that may be repeated as required. The results will not be entered in the CRF/database and will not be reported in the CTR. Except for drug screening, it is planned to perform these tests at screening only. Drug screening will be performed at screening and prior to dosing at Visit 2.

Table 5.2.3: 2 Exclusionary laboratory tests

E	T4
Functional lab group	Test name
Drug screening (urine)	Amphetamine/MDA
8 8( )	Barbiturates
	Benzodiazepine
	Cannabis
	Cocaine
	Methadone
	Methamphetamines/MDMA/XTC
	Opiates
	Phencyclidine
	Tricyclic antidepressants
Infectious serology (blood)	Hepatitis B surface antigen (qualitative)
	Hepatitis B core antibody (qualitative)
	Hepatitis C antibodies (qualitative)
	HIV-1 and HIV-2 antibody (qualitative)

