# 7.3.4 Safety analyses

Safety will be assessed as defined by the endpoints listed in Section 2.1.2 and 2.2.2 based on the treated set (TS). Safety analyses will be descriptive in nature and will be based on BI standards.

Page 78 of 102

Proprietary confidential information © 2020 Boehringer Ingelheim International GmbH or one or more of its affiliated companies

For all analyses the treatment actually administered (= treatment at onset) to the subject will be used (any deviations from the randomised treatment will be discussed in the minutes of the Report Planning Meeting).

Treatments will be compared in a descriptive way. The placebo group in the safety evaluation will consist of all subjects treated with placebo, regardless of the dose group in which they were treated. The test treatment groups will be compared to the placebo group in a descriptive way. Tabulations of frequencies/proportions will be used for the evaluation of categorical (qualitative) data, and tabulations of descriptive statistics will be used to analyse continuous (quantitative) data.

Measurements (such as ECGs, vital signs, or laboratory parameters) or AEs will be assigned to treatments (see Section 4.1) based on the actual treatment at the planned time of the measurement or on the recorded time of AE onset (concept of treatment-emergent AEs). Therefore, measurements planned or AEs recorded prior to intake of trial medication (part I) or prior to *first* intake of trial medication (part II) will be assigned to the screening period, those between the (first) trial medication intake and end of REP (see Section 1.2.2) will be assigned to the treatment period. Events occurring after the REP but prior to trial termination date (part I and II) or prior to second or third treatment period (part II) will be assigned to 'follow-up'. These assignments including the corresponding time intervals will be defined in detail in the TSAP. Note that AEs occurring after the last per protocol contact but entered before database lock will be reported to Pharmacovigilance only and will not be captured in the trial database.

Additionally, further treatment intervals (called analysing treatments) may be defined in the TSAP in order to provide summary statistics for other than above periods, such as combined treatments, on-treatment totals, or periods without treatment effects (such as screening and post-study intervals).

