#### 7.6 RANDOMISATION

In part I of the trial, the first 4 subjects of each dose level will not be randomised to maintain a treatment sequence of active-placebo (Cohort 1) active-active (Cohort 2) due to safety reasons. The remaining 4 subjects of each dose level (i.e., Cohort 3) will be randomised in a 3:1 ratio (test treatment to placebo). More details to the cohorts can be found in Section 3.1.

In part II of the trial, subjects will be randomised to one of the 3 treatment sequences R-T1-T2, T1-T2-R or T2-R-T1 in a 1:1:1 ratio. The block size will be documented in the CTR.

The sponsor will arrange for the randomisation as well as packaging and labelling of trial medication. The randomisation list will be generated using a validated system that uses a pseudo-random number generator and a supplied seed number so that the resulting allocation is both reproducible and non-predictable.

The randomisation list will contain additional blocks to allow for subject replacement (refer to Section 3.3.5).

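### SAP 6.1 applies the AE on-treatment phase to measurements, so in Part II the only scheduled post-dose value of 20 laboratory tests is attributed to the third-period treatment (4 of 12 subjects each, one sequence)

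*SAP*

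**What the plan says.** SAP 6.1 introduces its phases with the words "The following separate study phases will be defined for the analyses of AEs". In Part II each treatment's phase runs from dosing "until next administration or 0.00 h (midnight) on the day after trial completion date, whatever occurs first". No follow-up phase is defined. The same section then extends the phases beyond AEs: "Tables of vital signs, ECG and laboratory values will present results by the above mentioned on treatment phase".

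The protocol has two rules. Section 1.2.2 sets the REP at 8 days and, for AEs, goes further: "All AEs reported between administration of BI 706321 and the individual subject's end of trial will be counted as on-treatment AEs". Section 7.3.4 deals with measurements (ECG, vital signs, laboratory) and AEs together. It says that "those between the (first) trial medication intake and end of REP (see Section 1.2.2) will be assigned to the treatment period", with what follows going to follow-up, and it leaves the detailed definition of these assignments to the SAP.

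SAP 4 states that all analyses are as planned in the protocol. SAP 7.8 sorts Part II safety results by treatment sequence unless otherwise stated.

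**The concern.** The AE rule is not in dispute: the protocol states it and the SAP repeats it. The difficulty is that a rule written for AEs is carried over to planned measurements, for which the protocol has a different cut-off, and the change is not acknowledged.

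In most crossover safety tables this would matter little, because each period has its own samples. In Part II it matters for the tests measured only once after dosing. That single end-of-trial value has to go somewhere, and SAP 6.1 puts it under the last treatment received. The table then shows on-treatment results for tablet fasted, tablet fed and capsule fasted that come from three different sets of subjects. A reader could take them for a within-subject comparison, which the sampling schedule does not provide.

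**Working it through.** The plan gives no figure on this point, so there is none to reproduce. The counts come from the protocol's schedule and laboratory table.

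**1. Part II laboratory schedule** (protocol Flow Chart, Part II): set A at screening, set B at 24 h in each of the three periods, set C once at end of trial, Day 8 to 22.

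**2. Tests in set C but not set B** (protocol Table 5.2.3: 1):
- Blood: alkaline phosphatase, gamma-GT, glucose, total protein, haptoglobin, ferritin, uric acid, total cholesterol, triglyceride, chloride, phosphate = 11.
- Urine stick: nitrite, protein, glucose, ketone, urobilinogen, bilirubin, erythrocytes, leucocytes, pH = 9.
- Total 11 + 9 = 20. Rows done only on condition (manual differential, CK-MB, sediment) and TSH (set A only) are not counted.

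For these 20 tests the end-of-trial sample is the only scheduled post-dose value.

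**3. Where SAP 6.1 puts that sample.** Protocol 7.6: "subjects will be randomised to one of the 3 treatment sequences R-T1-T2, T1-T2-R or T2-R-T1 in a 1:1:1 ratio". The treatment in period 3 is:

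| Sequence | Third treatment | Subjects (12/3) |
|---|---|---|
| R-T1-T2 | T2 | 4 |
| T1-T2-R | R | 4 |
| T2-R-T1 | T1 | 4 |

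Each treatment is third in exactly one sequence. Each column holds 4 of 12 subjects, all from one sequence, and no subject contributes to two columns. The other 8 of 12 (66.7%) have no scheduled value.

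**4. Position relative to the REP.** With dosing on Day 1, Day d is (d - 1) x 24 h after the third dose. Day 8 = 168 h, Day 9 = 192 h, Day 22 = 504 h. If the REP ends at 8 x 24 = 192 h, visits on Days 8 and 9 are within it and visits on Days 10 to 22 are after it. That is 22 - 10 + 1 = 13 of the 22 - 8 + 1 = 15 allowed days. Under protocol 7.3.4 those later samples are follow-up; under SAP 6.1 they are on-treatment.

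**5. Percentages, conditional.** SAP 7 bases frequency percentages on all subjects in the set, with or without a value. If that rule governs laboratory frequency tables, one abnormal result among four tested prints as 1/12 = 8.3% rather than 1/4 = 25%, with 8 subjects in the missing category.

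**6. Part I for contrast.** The end-of-trial visit (Day 15 to 22, 336 to 504 h) always lies after the REP, so the labelling conflict is there too. But set C is also taken at 24 h and 168 h, so these tests have in-period values, and each subject has only one treatment.

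**The case against.** - **The protocol leaves the intervals to the SAP.** Section 7.3.4 does so for measurements as well as AEs, allows further intervals, and its follow-up sentence speaks of events. This has some force: the SAP could have chosen another cut-off. But defining assignments in detail is not the same as replacing a stated cut-off without saying so, and SAP 4 declares no change. The single-sequence columns arise whichever cut-off the SAP was free to choose.
- **The sparse data come from the flow chart, not the SAP.** True. No relabelling creates in-period values. The SAP decides only whether the table presents them as by-treatment results.
- **The effect would be visible.** Continuous summaries show N, the missing category is displayed when values are missing, and individual listings carry visit and actual treatment. This stands. A reader might infer that abnormality rates will be silently diluted threefold. The documents do not support that: SAP 7.8.2 names no abnormality-percentage table, it defers to a sponsor laboratory standard that is not available, and the 8 missing subjects would be shown.
- **Unseen documents may already handle this.** SAP 6.1 refers details to a technical analysis-dataset plan and a reviewer's guide, which could separate the end-of-trial visit. The SAP text does not.
- **Visits may be early.** A reader might infer from 13 of 15 days that most samples fall after the REP. That counts calendar days, not subjects. The spread of visits is unknown, and protocol 1.2.2 places the Part II end of trial at 8 days, so early visits are plausible. A Day 8 or 9 sample is on-treatment under the protocol too.
- **End-of-trial values of set B tests might be merged with the 24 h values.** The SAP does not say whether laboratory tables separate visits, so merging cannot be asserted.

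**Conclusion.** The point holds as a minor correction. SAP 6.1 applies an AE phase to measurements although protocol 7.3.4 ends their treatment period at the 8-day REP, and no change is recorded. For 20 tests in Part II, the result is by-treatment columns of 4 of 12 subjects, each from a single sequence, in which treatment cannot be separated from sequence. Any sample after the REP is also mislabelled as on-treatment.

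This rests on 12 completers (4 per sequence), scheduled samples only, Day 8 to 22 counted from the third dose, and a REP ending at 192 h. A subject who stops early has the end-of-trial sample under the last treatment received. Replacements (up to 4) or unscheduled retests could shift the counts.

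It would be wrong to read this as a threat to the trial's conclusions. The Part I primary endpoint is based on AEs and the Part II primary endpoints are PK. ALT, AST and bilirubin, which define the hepatic-injury AESI, are in set B and so measured in every period. Safety is descriptive, and no planned inference uses the affected columns.

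**What to change.** In SAP 6.1, leave the AE phases as they are. For vital signs, ECG and laboratory values, apply the protocol 7.3.4 cut-off: on-treatment to the end of the REP, later samples to follow-up.

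Show the Part II end-of-trial visit as its own time point, pooled over treatments, with percentages based on subjects tested. Flag Day 8 and 9 samples as within the REP. Pooling those is a display choice that goes beyond protocol 7.3.4, which assigns them to the treatment period, so record it in SAP 4.

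State in SAP 4 or 6.1 that AEs and measurements use different cut-offs, and reconcile 6.1 (by treatment phase) with 7.8 (sorted by sequence). Confirm that the technical dataset plan and the laboratory standard follow the same rule.

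The cost is a few lines of SAP text and one table column: no protocol amendment, no new samples, no new data. The downside is that Part II then shows few or no by-treatment values for these 20 tests, which is all the sampling schedule supports.
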